2 OBJECTIVES

2.1 Primary Objective

To determine the efficacy of the combination of lenvatinib and pembrolizumab in Black participants.

2.2 Secondary Objectives

- 2.2.1 Determine median PFS in the study population
- 2.2.2 Determine the incidence of treatment-related AEs in the study population
- 2.2.3 Determine the number of patients who discontinue treatment due to treatment-related AEs

2.3 Exploratory Objectives

- 2.3.1 Explore patient-reported outcomes of health related quality of life (EORTC-QLQ-C30+EN24), anxiety and depression (HADS), and financial toxicity (FACIT COST) in the study population

- 2.3.2 Explore ancestral markers and microbiome and cytokine/growth factor levels in blood, urine, and vaginal samples in Black patients with recurrent endometrial cancer undergoing treatment with lenvatinib and pembrolizumab

3 STUDY DESIGN

3.1 General Description

This study is a single-arm, open-label, multicenter phase 2 trial designed to prospectively evaluate the safety and efficacy of lenvatinib in combination with pembrolizumab for mismatch repair-proficient recurrent endometrial cancer in Black patients (a population under-represented on 2 FDA registration trials). Up to 100 patients will be treated at up to 10 sites throughout the United States. All patients will receive lenvatinib and pembrolizumab while participating in the study. Patients will continue to receive lenvatinib and pembrolizumab until their disease progresses or they experience unacceptable toxicity.

3.2 Primary Endpoint

ORR at 24 weeks in Black patients with recurrent endometrial cancer treated with lenvatinib 20 mg orally daily in combination with pembrolizumab 200 mg IV every 3 weeks

3.3 Secondary Endpoints

- 3.3.1 Proportion of patients who are alive and have not had disease progression or relapse following last dose of study treatment
- 3.3.2 Using criteria in the National Cancer Institute Common Terminology Criteria for Adverse Events Version 5.0 (CTCAE v5.0), all AEs captured as described in Section [8.4](#).
- 3.3.3 Number of patients who discontinue treatment due to treatment-related AEs.

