1.3 Study Rationale

Until recently, microsatellite stable (MSS) recurrent endometrial cancer was a disease of high unmet medical need. In 2018, the US Food and Drug Administration (FDA) granted a breakthrough designation and, in 2019, an accelerated approval to the combination of the immune checkpoint inhibitor, pembrolizumab, and the oral anti-angiogenic agent, lenvatinib.

With an objective response rate (ORR) at 24 weeks of 36.2% (95% CI, 26.5% to 46.7%) in patients with MSS tumors (n = 94), and a median duration of response (DOR) of 21.2 months (95% CI, 7.6 months to not estimable), compared to historical ORR of 12-15% and DOR of 3-6 months, these results were exciting and led to widespread adoption of the combination in clinical practice. This enthusiasm was despite the incidence of grade 3 or 4 treatment-related adverse events (AEs) in 83/124 (66.9%) patients--most commonly hypertension and diarrhea—a 33% discontinuation rate for toxicity, and absence of quality of life data. A confirmatory phase 3 trial of lenvatinib/pembrolizumab versus standard chemotherapy in the second-line setting recently reported a progression-free survival (PFS) and overall survival (OS) advantage for the lenvatinib/pembrolizumab combination but again with significant AEs and treatment discontinuation (33% vs 8% for chemotherapy). On July 21, 2021, the FDA approved pembrolizumab in combination with lenvatinib for patients with advanced endometrial carcinoma that is not microsatellite instability-high (MSI-H) or mismatch repair deficient (dMMR), who have disease progression following prior systemic therapy in any setting and are not candidates for curative surgery or radiation.

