6.5.2 Ongoing Follow-up

Patients who discontinue treatment with ongoing SD, PR, or CR (see Section 10) remain in follow-up status for PFS by reported clinical status every 3 months until one of the following occurs: disease progression, relapse, or death.

All patients will be followed for OS status every 3 months, until death or off-study.

The primary reason(s) for a patient's discontinuation from study treatment and from follow-up status are to be recorded in the source documents and the OnCore database.

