13 STATISTICAL CONSIDERATIONS

13.1 Study Design and Analysis

Primary Analysis: The binary outcome ORR: will be estimated with a sample proportion and 95% Wilson confidence intervals. The ORR will be estimated in unadjusted and adjusted manners, where in the latter case we use logistic regression to model the outcome against fixed effects for patient characteristics and disease biomarkers, using a Bernoulli distribution and logit link function, including a set of measurements that minimize the Bayesian Information Criterion.

Secondary Analyses: OS is calculated as the time between treatment start date until date of death from any cause or until censoring. PFS is calculated as the time between treatment start date until occurrence of disease progression or until censoring. The Kaplan-Meier product limit approach will be used to estimate step functions for OS and PFS. Proportional hazard modeling will be used to estimate mean survival time in both unadjusted and adjusted manners, where in the latter case we account for patient characteristics and disease biomarkers.

Safety Analyses: Times to toxicity, dose reduction, or drug discontinuation will be used as safety outcomes. Each measure is calculated as the time between treatment start date until event occurrence or until censoring. These measures will be summarized using proportional hazards regression, and visually present the event curves with cumulative incidence curves.

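### Secondary endpoint 3.3.1 is a proportion tied to the last dose with no time point, so it matches neither the median-PFS objective (2.2.1) nor the PFS analysis in 13.1

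*Combined protocol and SAP*

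**What the plan says.** Four parts of the combined protocol and SAP bear on this.

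- Section 2.2, objective 2.2.1: "Determine median PFS in the study population".
- Section 3.3, endpoint 3.3.1, the counterpart of that objective: "Proportion of patients who are alive and have not had disease progression or relapse following last dose of study treatment". No time point is given, and section 13 contains no analysis of this proportion.
- Section 13.1: "PFS is calculated as the time between treatment start date until occurrence of disease progression or until censoring". The estimator follows: "The Kaplan-Meier product limit approach will be used to estimate step functions for OS and PFS". Neither a median nor its confidence interval is mentioned, and death is not named as a PFS event.
- Section 3.1: "Patients will continue to receive lenvatinib and pembrolizumab until their disease progresses or they experience unacceptable toxicity". Section 9.1.4 gives the same duration.

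Section 6.5.2 covers patients who stop with stable disease or a response. They "remain in follow-up status for PFS by reported clinical status every 3 months until one of the following occurs: disease progression, relapse, or death".

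**The concern.** The endpoint differs from its objective and from the analysis on both the measure (a proportion against a time) and the clock (last dose against first dose). The last-dose anchor also fits poorly with treatment to progression. When progression is what ends treatment, the patient has already failed at the last dose. Patients still on treatment, often those doing best, have no last dose, and the wording does not say how to classify them. Successes can then come only from patients who stopped before progressing, for toxicity, by choice or for another reason in section 6.4.

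This is the only efficacy measure in the secondary endpoint list. Reported as worded, it would not answer objective 2.2.1. With 3.3.1 and 13.1 both in the plan, the report could present either one as the PFS result.

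**Working it through.** **The plan's own figures.** None is given for PFS or for 3.3.1. The only precision figure is ±0.1 for ORR in 13.2. It reproduces (1.96 × √(0.5 × 0.5/100) = 0.098) but has no bearing here.

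**Inputs.** Section 1.3 reports a "33% discontinuation rate for toxicity" for the combination, and 33% against 8% in the phase 3 trial, where 8% belongs to the chemotherapy arm. Section 9.2.11 reports that 19% of 94 patients discontinued pembrolizumab for adverse reactions. Section 13.2 projects 25 to 42 months of recruitment. The median PFS of this regimen is not in the documents, so m = 5, 7, 10 and 13 months are assumptions.

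**Model (assumed).** Time to progression or death is exponential with rate λ = ln 2/m. Early stopping is an independent exponential with rate μ = λf/(1 − f), so that a share f stops before progression.

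**Check 1: the proportion t months after last dose, once everyone has stopped.** The formula is f × 2^(−t/m).
- At t = 0 this is f. With f = 33% it is 33% at m = 5, 7, 10 and 13, so it says nothing about the median. With f = 0 it is 0%.
- At m = 7, moving f from 8% to 33% to 50% moves the proportion from 8% to 33% to 50%. Simulated median PFS from treatment start stays at 6.98, 7.01 and 7.00 months.
- At f = 33% and m = 7 it is 33%, 25%, 18% and 10% at t = 0, 3, 6 and 12 months. Without a time point it has no single value.

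**Check 2: a fixed cut-off of 18 months after start, under three ways of handling on-treatment patients.** Let S = exp(−18λ) and G = exp(−18μ). Patients who stopped early and are progression-free make up s = S(1 − G). Patients still on treatment make up o = SG. The result is s if on-treatment patients are failures, s/(1 − o) if they are excluded, and s + o = S if they count as progression-free.

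| m, f | S | G | Failures | Excluded | Progression-free |
|---|---|---|---|---|---|
| 10 mo, 8% | 0.2872 | 0.8972 | 0.0295 | 0.0295/0.7424 = 0.040 | 0.287 |
| 5 mo, 33% | 0.0825 | 0.2926 | 0.0583 | 0.0583/0.9759 = 0.060 | 0.082 |
| 5 mo, 19% | 0.0825 | 0.5569 | 0.0365 | 0.0365/0.9541 = 0.038 | 0.082 |

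Comparing the first two rows, the shorter median scores about 2.0 times as high if on-treatment patients are failures and 1.5 times as high if they are excluded. If they count as progression-free, the order is correct and early stopping has no effect. With 19% in place of 33%, the comparison is 3.7% against 3.0%, 3.8% against 4.0%, and 8.2% against 28.7%.

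**Check 3: the most favourable reading still needs a cut-off.** Count on-treatment patients as progression-free, with m = 7, uniform accrual over A months and at least 6 months of follow-up (assumed). The proportion is [exp(−6λ) − exp(−(6 + A)λ)]/(λA). It is 20% for A = 25 and 13% for A = 42, at identical efficacy.

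**The case against.** The strongest reply is that nothing is lost. Section 13.1 starts PFS at treatment start and plans a Kaplan-Meier curve, from which a median can be read. Section 6.5.2 keeps following patients who stop without progression. This stands. A reader might infer from 3.3.1 that the trial cannot deliver median PFS, and the documents do not support that: the fault lies in the endpoint line and its disagreement with 2.2.1 and 13.1.

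A reader might also infer that 3.3.1 makes a regimen with half the median PFS look twice as good. That holds only if on-treatment patients are scored as failures, which the plan does not say. The 8% used for the comparison is the chemotherapy arm's rate. The 33% may include patients who stopped only one drug: section 9.2.11 caps stopping both drugs for adverse reactions at 19% in its 94 patients. At 19% the reversal nearly or fully disappears. The trial is single-arm, so it makes no ranking of its own, and endpoint 3.3.3 reports treatment-related discontinuations separately.

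Finally, section 6.4 does not list progression among its reasons for stopping and defers to a schema that is not in the text available. The treat-to-progression premise therefore rests on 3.1 and 9.1.4.

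These points limit the size of the problem. They do not make 3.3.1 a measure of PFS, nor give it a time point, a rule for on-treatment patients or an analysis.

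**Conclusion.** The point holds as a mismatch between endpoint, objective and analysis, and it should be corrected. As written, 3.3.1 does not measure objective 2.2.1. At last dose it equals the share who stopped before progression, whatever the median. Later it depends on the time chosen. At a fixed cut-off it depends on how on-treatment patients are classified.

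That it fails to measure PFS follows from the wording together with 3.1 and 9.1.4. The sizes rest on the assumed medians, stopping rates and independent exponential model. No single figure for the distortion, and no general direction, can be claimed. The roughly twofold reversal is one reading among three. Median PFS remains obtainable through 13.1.

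**What to change.** Two passages need to change together.

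1. Restate 3.3.1 as: *PFS, from first dose of study treatment to disease progression or death from any cause, whichever is first, summarised by the Kaplan-Meier median with 95% CI.*
2. Amend 13.1 so that PFS counts death from any cause as an event and the analysis reports the median with its 95% CI. Changing 3.3.1 alone is not enough. Section 13.1 names only progression, so a death without progression could be censored there, although 3.3.1 already requires patients to be alive and 6.5.2 ends PFS follow-up at death.

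A 24-week PFS rate is optional. An off-treatment measure, if wanted, should be listed separately as exploratory. No stated objective needs either one.

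The cost is a few sentences of text. No new data, visits or patients are needed, because 6.5.2 already supplies the follow-up and 13.1 the Kaplan-Meier analysis.

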3.4 Exploratory Endpoints

- 3.4.1 Effects of lenvatinib and pembrolizumab on patient-reported outcomes of health related quality of life (EORTC-QLQ-C30+EN24), anxiety and depression (HADS), and financial toxicity (FACT COST) in the study population
- 3.4.2 Genetic ancestry analysis, microbiome analysis, and levels of cytokines/growth factors in blood, and urine
- 3.4.3 Quantify patient-reported gendered racial microaggressions, in-group identification scale, and Africultural coping systems inventory and compare with allostatic load scores, inflammatory markers and treatment response.

3.5 Multicenter Site Participation

This study will be conducted at up to 10 sites across the United States. The VCU MCC Early Phase Development Department serves as the Coordinating Team.

4 PATIENT SELECTION

4.1 Inclusion Criteria

A patient must meet all of the following inclusion criteria to be eligible to participate in the study:

	Yes	No	N/A
4.1.1 Histologically and/or cytologically confirmed endometrioid, serous, clear cell, carcinosarcoma, or de-differentiated or undifferentiated endometrial cancer with radiographic and/or clinical evidence of disease progression			
4.1.2 Documented microsatellite stable disease as tested by either MSI PCR or DNA mismatch repair (MMR) by IHC			
4.1.3 Self-identify as being of predominantly (>50%) Black race, inclusive of Black, African-American, Black Hispanic (Afro-Latinx), African, or Afro-Caribbean ancestry			
4.1.4 Received, ineligible for (by investigator determination), or declined platinum containing chemotherapy			
4.1.5 Received no greater than 2 prior lines of therapy. Maintenance therapies and hormonal therapies will NOT count as a line of therapy. Patients may have received prior immune checkpoint inhibitor therapy or bevacizumab in one of the 2 prior lines of therapy.			
4.1.6 Measurable disease as determined by RECIST v1.1: 
At least one lesion of ≥ 10 mm in the longest diameter for a non-lymph node, or ≥ 15 mm in the short-axis diameter for a lymph node that is serially measurable using computerized tomography/magnetic resonance imaging (CT/MRI)Target lesions limited to a radiated field must show evidence of substantial size increase according to previous scans to be deemed a target lesion			
4.1.7 Eastern Cooperative Oncology Group (ECOG) performance status of 0 to 2 (see Appendix 1)			
4.1.8 Age ≥ 18 years			
4.1.9 Ability to swallow oral medications			

	Yes	No	N/A
4.1.10 Patients who are not postmenopausal or have not undergone hysterectomy must have a documented negative serum pregnancy test within 72 hours prior to initiating study treatment Note: Postmenopausal is defined as any of the following: 
• Age \geq 60 years• Age $<$ 60 years and amenorrheic for at least 1 year with follicle-stimulating hormone (FSH) and plasma estradiol levels in the postmenopausal range• Bilateral oophorectomy			
4.1.11 Patients of child-bearing potential must agree to use a medically accepted method for preventing pregnancy during and for a minimum of 4 months following the last dose of lenvatinib or pembrolizumab			
4.1.12 Patients with known brain metastases will be eligible if they have completed primary brain therapy (such as whole brain radiotherapy, stereotactic radiosurgery, or complete surgical resection) and if they have remained clinically stable, asymptomatic, and off of steroids for at least 28 days before starting study treatment			
4.1.13 Toxicities from previous cancer therapies resolved to grade ≤ 1 unless specified otherwise (exceptions: chronic residual toxicities that in the opinion of the investigator are not clinically relevant, given the known safety/toxicity profiles of Lenvatinib and pembrolizumab, such as alopecia, grade ≤ 2 anemia; neuropathy related to previous chemotherapy must be resolved to grade ≤ 2)			
4.1.14 Ability to understand and the willingness to sign a written informed consent document			

4.2 Exclusion Criteria

A patient who meets any of the following exclusion criteria is ineligible to participate in the study:

	Yes	No	N/A
4.2.1 Endometrial leiomyosarcoma or endometrial stromal sarcoma			

		Yes	No	N/A
4.2.2	Unstable central nervous system (CNS) metastases			
4.2.3	Gastrointestinal malabsorption, gastrointestinal anastomosis, or any other condition that might affect the absorption of lenvatinib			
4.2.4	Pre-existing grade ≥ 3 gastrointestinal or non-gastrointestinal fistula			
4.2.5	Radiographic evidence of major blood vessel invasion/infiltration			
4.2.6	Clinically significant hemoptysis or tumor bleeding within 2 weeks prior to the first dose of study treatment			
4.2.7	History of congestive heart failure greater than New York Heart Association (NYHA) Class II, unstable angina, myocardial infarction, cerebrovascular accident, stroke, or cardiac arrhythmia associated with hemodynamic instability within 12 months of the first dose of study treatment			
4.2.8	Known history or evidence of interstitial lung disease or active, non-infectious pneumonitis			
4.2.9	Administration of or condition requiring administration of systemic steroid therapy or any other form of immunosuppressive therapy within 7 days prior to initiating study treatment Exception: Patients with conditions that can be managed with steroids equivalent to or less than an oral prednisone dose of 10 mg daily are not excluded from the study			
4.2.10	Active autoimmune disease (with the exception of psoriasis) that has required systemic treatment in the past 2 years (ie, with use of disease-modifying agents, corticosteroids, or immunosuppressive drugs) or a documented history of clinically severe autoimmune disease or a syndrome that requires systemic steroids or immunosuppressive agents Note: Patients with the conditions or medical history listed below are not excluded from the study. 
• Vitiligo• Resolved childhood asthma/atopy• Requirement for intermittent use of bronchodilators or local steroid injections or topical steroids			

	Yes	No	N/A

 • Hypothyroidism stable on hormone replacement • Sjogren's Syndrome 			
4.2.11 Has received >2 prior systemic chemotherapy regimen (other than adjuvant or neoadjuvant) for endometrial cancer; participants may receive up to 2 regimens of platinum-based chemotherapy in total, as long as one is given in the neoadjuvant or adjuvant treatment setting			
4.2.12 Prior anticancer treatment within 28 days of study start			
4.2.13 Has received prior treatment with an agent directed to a stimulatory or co-inhibitory T-cell receptor other than an anti-PD-1, anti-PD-L1, or anti-PD-L2 agent, and who has discontinued from that treatment due to a grade 3 or higher immune-related adverse event (irAE)			
4.2.14 Has received prior radiation therapy within 21 days of study start with the exception of palliative radiotherapy to bone lesions, which is allowed if completed 2 weeks before study start; participants must have recovered from all radiation-related toxicities and/or complications prior to randomization			

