1.3.1 Rationale for Version 3 Changes

In patients with advanced or recurrent endometrial cancer, the addition of pembrolizumab to standard chemotherapy resulted in significantly longer progression-free survival than with chemotherapy alone. In the mismatch repair-proficient cohort, median progression-free survival was 13.1 months with pembrolizumab and 8.7 months with placebo (hazard ratio, 0.54; 95% CI, 0.41 to 0.71; $P<0.001$) ([17](#))

Dostarlimab plus carboplatin–paclitaxel significantly increased progression-free survival among patients with primary advanced or recurrent endometrial cancer. In the overall population, progression-free survival at 24 months was 36.1% (95% CI, 29.3 to 42.9) in the dostarlimab group and 18.1% (95% CI, 13.0 to 23.9) in the placebo group (hazard ratio, 0.64; 95% CI, 0.51 to 0.80; $P<0.001$). Overall survival at 24 months was 71.3% (95% CI, 64.5 to 77.1) with dostarlimab and 56.0% (95% CI, 48.9 to 62.5) with placebo (hazard ratio for death, 0.64; 95% CI, 0.46 to 0.87). ([18](#))

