4.2.18 History of solid organ or allogeneic stem cell transplant			
4.2.19 Known intolerance to either of the study drugs (or any of the excipients)			
4.2.20 Known immunodeficiency, eg, human immunodeficiency virus (HIV) Note: HIV testing is not required for eligibility screening			

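### The only entry criterion naming irAEs (4.2.13) exempts prior anti-PD-1/PD-L1/PD-L2 agents, so a resolved life-threatening irAE on another such agent is screened only by broad reading, partial organ cover or discretion

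*Combined protocol and SAP*

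**What the plan says.** Criterion 4.1.5 states: "Patients may have received prior immune checkpoint inhibitor therapy or bevacizumab in one of the 2 prior lines of therapy". It does not ask why that therapy ended. Section 1.3.1, the rationale for the Version 3 changes, shows that such patients are expected. It cites pembrolizumab added to first-line chemotherapy and also a second PD-1 agent: "Dostarlimab plus carboplatin–paclitaxel significantly increased progression-free survival".

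Criterion 4.2.13 excludes certain patients previously given a drug aimed at T-cell receptors. It applies where that drug was "other than an anti-PD-1, anti-PD-L1, or anti-PD-L2 agent, and who has discontinued from that treatment due to a grade 3 or higher" irAE. Both parts must hold: the agent lies outside the PD-(L)1 class, and it was stopped for a severe irAE.

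Other criteria that bear on the question:
- 4.1.13 requires "Toxicities from previous cancer therapies resolved to grade" 1 or lower, with listed exceptions.
- 4.2.7 excludes named cardiac histories, including "cardiac arrhythmia associated with hemodynamic instability within 12 months of the first dose of study treatment".
- 4.2.8 excludes "Known history or evidence of interstitial lung disease or active, non-infectious pneumonitis".
- 4.2.10 excludes certain active autoimmune disease and also "a documented history of clinically severe autoimmune disease or a syndrome that requires systemic steroids or immunosuppressive agents".
- 4.2.19 excludes "Known intolerance to either of the study drugs (or any of the excipients").
- 4.2.25 excludes conditions that the investigator thinks may raise the patient's risk.

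On study, Section 7.4, Table 4 and Appendix 2 say, event by event, when pembrolizumab is withheld and when it is stopped for good.

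**The concern.** Pembrolizumab is given to everyone in this trial. Section 9.2.10 describes immune-mediated reactions, some fatal, as a feature of the whole PD-1/PD-L1 blocking class. A severe reaction to another member of that class is therefore relevant history. Yet the one criterion that screens on irAE history asks about other T-cell agents and leaves this class out. The protocol gives no reason for treating a severe irAE on a PD-(L)1 agent as less important than one on a different T-cell agent.

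What is at stake is the safety of individual patients. Someone who had a life-threatening immune reaction to one PD-(L)1 agent could be given another without any criterion having put the question to the site. With up to 10 sites, judgement may also differ from one to the next.

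**Working it through.** No figure in the plan bears on this point and no arithmetic applies. The check is a worked case, followed by a comparison of the two on-study schedules.

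**Worked case.** A patient stopped dostarlimab for grade 4 colitis, has recovered to grade 1 or lower and is off steroids.

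| Criterion | Does it keep her out? |
|---|---|
| 4.1.5 | No. Prior checkpoint therapy is allowed. |
| 4.1.13 | No. It looks at present grade, and the event has resolved. |
| 4.2.7, 4.2.8 | No. They cover certain cardiac events, interstitial lung disease and active pneumonitis. |
| 4.2.9 | No. The steroid look-back is 7 days. |
| 4.2.10, active disease | No. The event is no longer active. |
| 4.2.10, documented history | Only if a resolved irAE is read as clinically severe autoimmune disease. |
| 4.2.13 | No. Dostarlimab belongs to the exempted class. |
| 4.2.19 | No. It concerns the study drugs, so it could reach prior pembrolizumab but not dostarlimab. |
| 4.2.25 | Only if the investigator so judges. |

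Had the event been myocarditis with hemodynamically unstable arrhythmia in the past 12 months, or a lung event recorded as interstitial lung disease, 4.2.7 or 4.2.8 would have caught it. That cover is real but specific to those organs.

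**Which events are permanent stops on study?** The two schedules do not always agree, so an entry rule should rest on events where they do.

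| Prior event | Section 7.4 / Table 4 | Appendix 2 |
|---|---|---|
| Grade 4, non-endocrine | Stop | Stop |
| Grade 3 pneumonitis | Stop | Stop |
| Grade 3 myocarditis | Stop | Stop |
| Grade 3 Guillain-Barré syndrome or encephalitis | Stop (neurological row) | Stop (named events) |
| Recurrent grade 3 needing systemic immunosuppression | Stop | Stop (row for all other irAEs) |
| Grade 2 myocarditis | Stop | Withhold |
| Grade 3 nephritis | Withhold | Stop |
| Liver enzymes or bilirubin | By multiples of the upper limit of normal | By grade; 3 or 4 is a stop |
| Grade 3 colitis | Withhold | Withhold |

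The first five rows are common ground and can be read from a recorded grade. One loose end: the colitis row of Appendix 2 has no entry for recurrence, so for recurrent grade 3 colitis the general rule in Section 7.4 decides. Endocrine events are handled more leniently in both schedules, with continuation or resumption possible once controlled.

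**The case against.** The strongest reply is that 4.2.10 already does the work. Its documented-history limb looks backward, has no time limit, and could reasonably be applied to a resolved grade 4 colitis or neurological event. The present tense of the verb belongs to the syndrome alternative and does not weaken that limb. This stands as arguable cover. It is not dependable cover, because 4.2.10 never mentions irAEs. Read broadly, it could also remove patients with steroid-treated grade 3 colitis, for whom Table 4 allows resumption.

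Second, 4.2.25 is a written exclusion that fits this patient, and the protocol has oversight: an eligibility attestation (5.1.2), monthly meetings (Section 14) and DSMC review (14.1.2). That is true. But 4.2.25 gives no threshold, the attestation confirms only the criteria as written, and the meetings and DSMC review are not described as checks of eligibility before dosing.

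Third, allowing rechallenge within the class may be deliberate, and the documents give no recurrence rate after a change of PD-(L)1 agent. This also stands. It argues for a narrow exclusion and against barring every patient who stopped such an agent for a grade 3 event.

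A reader might infer that the entry criteria contradict the on-study stopping rules. The documents do not support that. Table 4 is headed as recommended modifications, Appendix 2 leaves withholding or stopping to the investigator or treating physician, and both govern reactions to pembrolizumab during the study.

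**Conclusion.** The gap is real but narrow. No criterion names a prior irAE on an anti-PD-1, anti-PD-L1 or anti-PD-L2 agent. For an agent other than pembrolizumab, a resolved life-threatening event is screened only by the three partial routes described above. The conclusion rests on the literal wording of 4.2.13 and on the irAE having resolved before entry.

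Its size cannot be computed. The documents give neither the frequency of prior PD-(L)1 use among enrollees nor the rate of severe irAEs on it, and the number affected may be zero.

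Three stronger readings are tempting and should be resisted:
- A reader might infer bias in the ORR or the safety estimates. Nothing in the documents allows such an effect to be calculated, and none is claimed.
- A reader might measure the gap by counting Table 4 rows with a permanent stop and no matching entry criterion. Such a count treats hepatitis as two toxicities, sets aside the history limb of 4.2.10, and does not measure risk.
- A reader might cite grade 2 myocarditis as a clear permanent stop that entry overlooks. Appendix 2 only withholds for it, so it is not a settled example.

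This is a cheap improvement to patient protection. It does not undermine the trial's estimates.

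**What to change.** Leave 4.1.5 as it is, so that prior PD-(L)1 exposure remains eligible, and keep the current 4.2.13 rule for other T-cell agents. Add to 4.2.13 an exclusion for any irAE on a prior anti-PD-1, anti-PD-L1 or anti-PD-L2 agent that was:

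- (a) grade 4, other than an endocrinopathy controlled on replacement;
- (b) pneumonitis or myocarditis of grade 3 or higher;
- (c) Guillain-Barré syndrome or encephalitis of grade 3 or higher; or
- (d) recurrent grade 3 requiring systemic immunosuppression.

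A single resolved grade 3 colitis, and endocrinopathies stable on replacement, would stay eligible. Because the list uses recorded grade, and for (d) recurrence and treatment, sites would not need past laboratory multiples or steroid-taper records.

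The Section 12 calendar already collects history and baseline conditions. Within that, record for each prior checkpoint inhibitor the agent, the irAE, its grade and its outcome.

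The cost is a wording change to one criterion and a small addition to baseline data capture. The downside is possibly a few fewer eligible patients, a number the documents do not allow one to estimate.
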